At the completion of at least 2 weeks of run-in (with a minimum of at least 8 rescue inhaler usages) and with documentation of stable clinical status throughout run-in, the patient will return for baseline testing; including vital signs, health related quality of life and Anthonisen Exacerbation questionnaires, pre and post bronchodilator spirometry and 6-minute walk testing (see table/flow chart). Average Peak Inspiratory Flow (Baseline PIF) and average Number of Rescue Inhalations per day (Baseline Inhalations) will be determined from the Digihaler Dashboard Data downloads during run-in.

In the event that the patient does not meet number of rescue inhaler usages or does not have a stable clinical status during run-in, an additional 2 weeks of run-in may be obtained. If at the end of the extended run-in period so that Baseline PIF and Baseline Inhalations cannot be determined or the patient continues to be clinically unstable, the patient will be discontinued from the study. If the patient has an upper respiratory tract infection or COPD exacerbation during run-in, they will also be discontinued from the study. Patients may be re-screened one time at a later date, when stable.

Once run-in and baseline testing are complete, all patients will continue on their maintenance COPD medications and use the ProAir Digihaler rescue SABA exclusively for the next 6 months. Patients will be provided with paper forms of the CAT, BCSS and Anthonisen Exacerbation criteria, to be completed at home on a weekly basis and mailed to the research center upon completion).

Throughout the treatment period, all rescue inhaler usage will be electronically transmitted to, monitored at and downloaded from the Digihaler Dashboard by the research center on every other business day basis (Monday, Wednesday and Friday). At the completion of each Digihaler Dashboard Data Download, comparisons of Daily PIF (average PIF of all rescue inhalations in a day) and Daily Inhalations (number of rescue inhalations in a day) to Baseline PIF and Baseline Inhalations will be made.

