All patients with Daily Inhalations exceeding Baseline Inhalations by ≥ 4 Inhalations per day and/or with a Daily PIF $\leq 80\%$ of Baseline PIF for 2 consecutive days will be DEFINED as “at risk”. For each “at risk” event, the patient will be contacted, their health status reviewed, and CAT and Anthonisen Exacerbation questionnaires will be administered. Based on symptoms, patients may also be advised to seek additional medical care.

All patients will be contacted on a monthly basis, irrespective of “risk” findings and seen in person every 3 months. All medication usage (including ProAir Digihaler medication usage), changes in medical care, healthcare contacts and usage, and any adverse events will be recorded. All office records for the intervening time period will be reviewed and Information for any non-office healthcare contacts and usage will be requested to provide detailed clinical information for comparison to Digihaler usage records.

At months 3 and 6 on treatment, all subjects will return to the research center, where vital signs, Anthonisen Exacerbation and CAT questionnaires, and post bronchodilator spirometry will be assessed. All medication usage (including ProAir Digihaler medication usage), changes in medical care, healthcare contacts and usage, and any adverse events will be recorded. All office records for the intervening time period will be reviewed and Information for any non-office healthcare contacts and usage will be requested to provide detailed clinical information for comparison to Digihaler usage records. Three (3) new ProAir Dihgihalers will be dispensed at month 3.

Throughout the treatment period, all rescue inhaler usage will be electronically monitored and downloaded from the Digihaler Dashboard by the research center on an every other business day basis (Monday, Wednesday and Friday). At the completion of each Digihaler Dashboard Data Download, comparisons of Daily PIF (average PIF of all rescue inhalations in a day) and Daily Inhalations (number of rescue inhalations in a day) to Baseline PIF and Baseline Inhalations will be made.

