7. Correlation and regression analysis of PIF and/or Inhalations events at varying thresholds
 - a. Daily PIF 10, 20, 30 or 40% below Baseline PIF
 - b. Daily Inhalations at 2, 4 or 6 Inhalations above Baseline Inhalations
 - c. Daily PIF and/or Inhalations duration of 2, 3 or 4 or more days outside of Baseline
8. Frequency and duration of AEC events of 2 or more major symptoms (Type I and Type II)
9. Frequency and duration of BCSS events (increase in BCSS by 2 above Baseline BCSS)
10. Correlation and regression analysis of PIF, Inhalations and IV events with AEC events
11. Correlation and regression analysis of PIF, Inhalations and IV events with BCSS event
12. Correlation of Digihaler changes in PIF above baseline and changes in CAT
13. Correlation off changes in SABA use above baseline with changes in CAT
14. Correlation of Digihaler changes in Inhalation Volume above baseline with changes in CAT
15. Descriptive sub-group analysis of PIF, Inhalations and IV thresholds by FEV1 severity, GOLD groups and BODE at Baseline.

REFERENCES

1. World Health Organization. Global Health Estimates 2016: Deaths by Cause, Age, Sex, by Country and by Region 2000–2016. 2018 [accessed October 2020]. s
2. GOLD. Global Strategy for the Diagnosis, Management, and Prevention of Chronic Obstructive Pulmonary Disease. 2020 Report. www.goldcopd.org.
3. Nici L, et al. Pharmacologic Management of Chronic Obstructive Pulmonary Disease. An Official American Thoracic Society Clinical Practice Guideline Am J Respir Crit Care Med. 2020; 201:56-59.
7. van der Molen T, Miravitles M, Kocks JW. COPD management: role of symptom assessment in routine clinical practice. Int J Chron Obstruct Pulmon Dis. 2013; 8:461-471.

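### Events at the at-risk trigger prompt a patient contact while they may still be running, so item 7's comparison of 4-or-more-day events, and partly of 3-day events, is open to influence from the trial's own contact

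*Protocol*

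**What the plan says.** PLANNED ANALYSIS item 7 calls for "Correlation and regression analysis of PIF and/or Inhalations events at varying thresholds". It sets PIF at 10, 20, 30 or 40% below baseline, inhalations at 2, 4 or 6 above baseline, and, in 7c, "Daily PIF and/or Inhalations duration of 2, 3 or 4 or more days outside of Baseline".

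The Protocol Overview uses part of the same grid as an operational trigger. It covers "All patients with Daily Inhalations exceeding Baseline Inhalations by ≥ 4 Inhalations per day" and/or a Daily PIF at or below 80% "of Baseline PIF for 2 consecutive days will be DEFINED as" at risk. For each such event "the patient will be contacted, their health status reviewed, and CAT and Anthonisen Exacerbation questionnaires will be administered". It adds: "Based on symptoms, patients may also be advised to seek additional medical care".

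The comparison with baseline is made after each download, and data are "downloaded from the Digihaler Dashboard by the research center on every other business day basis (Monday, Wednesday and Friday").

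The secondary objectives seek an optimal threshold for characterising acute CAT changes. STATISTICAL ANALYSIS foresees sensitivity, specificity and ROC work and labels all data exploratory.

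**The concern.** The trigger (20% PIF loss or +4 inhalations, for 2 days) lies inside the grid that item 7 compares. Once an event reaches it, staff call the patient, review health status and may advise care. Whether that event then goes on to a third or fourth day, or deepens to 30-40% or +6, may depend partly on the call. The same holds for the weekly CAT, Anthonisen (AEC) and BCSS forms completed afterwards.

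The exposure is uneven. An event that stays at 10% or +2, or that shows only in inhalation volume (IV), prompts no at-risk contact. Thresholds are thus compared under different management, and none of the planned analyses distinguishes days or scores before contact from those after it. At stake is what the pilot can say about a longer-duration rule, or about a deeper cut reached late in an event.

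**Working it through.** The protocol gives no power, alpha or timing figure to reproduce. The check is how early contact can fall within an event.

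**Inputs from the Protocol Overview:** trigger met on the second consecutive qualifying day (event day 2); downloads on Monday, Wednesday and Friday; comparison after each download.

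**Assumptions, not in the protocol:** contact on the day of the download; event day 2 equally likely on each weekday; no late data transfer or failed call. The protocol does not say whether a download is taken to show the current day, so both readings are run:

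- Reading A: a download made on event day 2 already shows that day.
- Reading B: a download shows completed earlier days only.

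Contact day = 2 + number of days from event day 2 to the first download that shows it.

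| Event day 2 falls on | Mon | Tue | Wed | Thu | Fri | Sat | Sun |
|---|---|---|---|---|---|---|---|
| Contact on event day, A | 2 | 3 | 2 | 3 | 2 | 4 | 3 |
| Contact on event day, B | 4 | 3 | 4 | 3 | 5 | 4 | 3 |

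Counting across the seven weekdays:

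| | A | B |
|---|---|---|
| Contact by event day 3 | 6/7 (86%) | 3/7 (43%) |
| Contact by event day 4 | 7/7 (100%) | 6/7 (86%) |
| Day 3 complete before contact | 1/7 (14%) | 4/7 (57%) |
| Day 4 complete before contact | 0/7 | 1/7 (14%) |

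So nearly every trigger-level event of 4 or more days includes the contact. For 3 days the answer depends on the reading.

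**Illustration of what a contact effect would do (both inputs assumed).** Let q be the daily chance that an event continues, and e the relative cut in q from the day after contact. The step from day m−1 to day m has probability q(1−e) if contact came by day m−1, and q otherwise. Average over the seven weekdays. With q = 0.75 and no effect, 75% of 2-day events reach day 3 and 0.75 × 0.75 = 56% reach day 4.

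With e = 0.5, so that q(1−e) = 0.375:

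- A, day 3: (3/7)(0.375) + (4/7)(0.75) = 59%.
- A, day 4: (3/7)(0.375 × 0.375) + (3/7)(0.75 × 0.375) + (1/7)(0.75 × 0.75) = 26%.
- B, day 3: no contact falls before day 3, so 75%, unchanged.
- B, day 4: 0.75 × [(3/7)(0.375) + (4/7)(0.75)] = 44%.

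With e = 0.25 the day-3 and day-4 shares are 67% and 40% (A), or 75% and 50% (B). The day-4 share for q from 0.6 to 0.9 is:

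| q | No effect | e = 0.25, A / B | e = 0.5, A / B |
|---|---|---|---|
| 0.6 | 36% | 25% / 32% | 17% / 28% |
| 0.75 | 56% | 40% / 50% | 26% / 44% |
| 0.9 | 81% | 57% / 72% | 38% / 64% |

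These rows show sensitivity only. The protocol supports no value of q or e, nor that e exceeds zero.

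**The case against.** The case against has real weight.

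- **Longer events are not seen only after the trial has acted.** A reader might infer this, but day 3 is complete before contact for 1/7 to 4/7 of weekdays, and late transfers or missed calls would raise that share. An event already at 30-40% or +6 on days 1 and 2 is fully observed before contact; only later deepening is exposed. This stands.
- **True signals are not shown to become false positives.** The tempting argument is that successful care leaves a short event followed by a normal CAT. But the CAT and Anthonisen forms are administered at the contact itself, before any advised care can act. Item 5 defines a CAT event as a rise of 2 points over baseline without limiting it to weekly forms. A symptomatic patient can therefore register an event at the call. This stands.
- **Contact is certain but care is not.** Advice depends on symptoms and is worded as a possibility, so the size and direction of any effect are unknown. This stands.
- **Much is already recorded.** The Protocol Overview collects changes in care, healthcare contacts and outside records for comparison with inhaler usage, and healthcare utilisation is a listed variable. This stands in part: no date for the at-risk contact is named, nor a link from it to resulting care.
- **It is an exploratory pilot of 20 patients, and details belong in an analysis plan.** This lowers the stakes and excuses the missing power. It does not remove the interaction between two rules that the protocol itself fixes, and a later analysis plan cannot recover dates that were not captured.

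**Conclusion.** The point holds for events that meet the at-risk trigger. Item 7's comparison of durations is open to influence from the trial's own contact, chiefly for 4 or more days (contact by day 4 for 6/7 to 7/7 of weekdays) and partly for 3 days (contact by day 3 for 3/7 to 6/7). Deepening after contact and later weekly CAT, AEC and BCSS scores are exposed in the same way. These shares rest on same-day contact and equal weekday frequency, and they describe the timing of a call, not the size of a bias.

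A reader might go further and conclude that the longer or deeper categories hold mostly events where nobody acted or action failed, or that any threshold drawn from item 7 is biased in a known direction. The protocol supports neither: it gives no figure for how often care follows contact or what contact does to an event.

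**What to change.** Leave the contact rule unchanged.

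1. Record the date of each at-risk contact and of any resulting care or treatment change, linked to the event that prompted it.
2. Classify each event by onset date (first qualifying day) and by the depth reached before contact.
3. In items 6, 7, 10 and 11, add a sensitivity analysis that flags event days and questionnaires after contact. Contact could enter as a time-varying covariate, or the analysis could use pre-contact days plus the CAT and AEC taken at the contact, before any advised care.
4. Report contact-prompted care descriptively. Do not count it as a deterioration outcome in the threshold comparison: only trigger-level events can prompt it, so counting it would favour the trigger over 10% and +2 by construction.
5. Qualify any statement about 3-day or 4-or-more-day rules by that analysis.

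The cost is two linked dates per event and one extra analysis. The downside is that fewer days inform the longer-duration rules. Restricting at contact may itself be informative, because advice to seek care depends on symptoms. The analysis therefore belongs beside the planned one, not in its place.

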Study Title:

ProAir Digihaler in COPD Disease Management: A real world study to assess ProAir Digihaler inhalation parameters thresholds and their use to identify deterioration in clinical practice

Study Site:

Pulmonary Research Institute of Southeast Michigan between May 19, 2021 and June 20, 2022

Study NCT #: NCT04821869

Advarra IRB Approval: Mar 30, 2021

Title: ProAir Digihaler in COPD Disease Management: A real world study to assess ProAir Digihaler inhalation parameters thresholds and their use to identify deterioration in clinical practice

Primary Investigator: [name].

Teva Collaborating Investigators: [name]., [name]

Background: Despite increasing awareness of the problems and needs, COPD remains the 3rd leading cause of death in the world and has significant impacts on patient function and quality of life. Even in those patients diagnosed with COPD, management is very poor, with over half of COPD exacerbations never reported. In addition, patients who do seek medical attention often delay reporting when they have symptoms of exacerbations. The consequences of these events are well known, with negative impacts on lung function, symptoms, quality of life, future exacerbations and increased mortality. Finding a way to assist patients and caregivers to better identify deterioration in COPD and improve disease management is essential to overcoming these issues.

Proposal:

A pilot study to explore the utilization of the TEVA ProAir Digihaler rescue medication use and inhalation parameters to identify disease deterioration to help in the management of COPD patients in clinical practice.

This study is designed to follow a small sample size of patients with COPD, monitor and collect inhalation parameters from the DIGIHALER dashboard, and changes in symptom control as measured by the COPD Assessment Test (CAT) to identify potential inhalation parameter thresholds that could be applied to the management of patients with COPD in clinical practice.

Objective(s):

Primary Objective:

- 1) Identify trends in Peak Inspiratory Flow (PIF) rates that associate with disease deterioration as defined by loss of symptom control and reduced lung function in patients with COPD.

Secondary Objectives:

- 1) Describe specific changes in ProAir Digihaler PIF (e.g. 10, 20, or 30% reduction in PIF from baseline for a minimum of 2 consecutive days) to identify an optimal threshold for characterizing trends in acute changes in the COPD Assessment Test (CAT)

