The number of albuterol rescue inhalations used and measured over 2 weeks at baseline using the Digihaler device. Baseline inhalations per day at baseline will be derived by the total number of inhalations divided by the total number of days during the baseline period and reported as inhalations per day or Baseline Inhalations/day.
3. Baseline Inhalation Volume (**Baseline IV**) measured via Digihaler device
IV is the volume of air inhaled during an albuterol rescue inhalation effort, expressed in Liters. Individual IV measurements collected over 2 weeks at baseline will be measured using the Digihaler device. The mean value for IV during the baseline period will be reported as the Baseline IV.

Protocol Overview

The trial is an unblinded open label single center study designed to identify trends in Peak Inspiratory Flow (PIF) rates and Rescue Albuterol Inhaler usage (Inhalations) that associate with disease deterioration as defined by worsening of symptoms and reduced lung function in patients with COPD.

The study will consist of a run-in period of approximately 2 weeks, a treatment period of 6 months and a follow-up period of 1 week. Twenty (20) patients with COPD requiring intermittent short acting beta agonist (SABA) rescue inhaler usage, but not requiring frequent SABA nebulizer rescue usage, will be enrolled.

After signing informed consent, patients will undergo a screening evaluation. During the run-in period, patients will continue on their COPD maintenance treatments, while discontinuing all previously prescribed periodic use rescue medications. Upon completion of screening, all patients will be dispensed a ProAir Digihaler to be used exclusively as their rescue medication throughout the duration of the study. During the run-in period all rescue inhaler usage will be electronically monitored and patient data from the Digihaler Dashboard will be downloaded every other business day basis (Monday, Wednesday and Friday).

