If a serious adverse event occurs, the Institutional IRB will be notified within five business days of awareness of the event by the investigator. The study coordinator may initiate the IRB notification, but it must be filed by the study investigator or co-investigators. If the serious adverse event is fatal or life threatening, notification to the Institutional IRB must be made within 24 hours, irrespective of the extent of available adverse event information. This timeframe also applies to additional new information (follow-up) on previously forwarded serious adverse event reports.

The MedWatch 3500A form should be utilized to report serious adverse events to the FDA.

All adverse events (serious and non-serious) will be reported on the adverse event page(s) of the CRF. Adverse events should be reported using concise medical terminology on the CRFs. Non-serious AE's will be reported annually to the IRB as appropriate.

STATISTICAL ANALYSIS

Primary Outcome Measure:

- 1) Change in Peak Inspiratory Flow (PIF) from Baseline as measured via the ProAir Dihaler device

Secondary Outcome Measures:

1. Change in SABA use (Inhalations) from Baseline
2. Change in Inhalation Volume (IV) from Baseline
3. Change in CAT
4. Change in FEV₁

Other Outcome Measures:

1. Change in Anthonisen Exacerbation Criteria
2. Change in BCSS
3. Change in Inhalation Volume

All data is exploratory, with no calculated power or expected predictive probabilities. Statistical thresholds, comparisons, correlations and regressions, sensitivity/specificity/ROC analysis will be performed using Wizard 1.9.45 Statistics. Additional statistical analysis may be performed as per TEVA biostatistics.

PLANNED ANALYSIS

1. Average of PIF value and number of PIF events at 10%, 20%, 30%, 40% below Baseline PIF for 2 or more days per patient
2. Average summary statistics PIF values and frequency of PIF events across all patients
3. Number of inhalations per day that are 4 or more Inhalations above Baseline Inhalations for 2 or more days
4. Frequency of IV events that are 20% below Baseline (see Derived measurements) for 2 or more days
4. Frequency of combined events of PIF and IV 20% below Baseline and 4 or more Inhalations per day above Baseline for 2 or more days combined
5. Frequency of CAT events (defined as increase in CAT score by 2 above Baseline CAT score)
6. Correlation and regression analysis of PIF, Inhalations and IV events with CAT events

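### A threshold chosen as optimal and scored in the same 20 patients is expected to look better than it is, and the protocol names no correction for the selection

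*Protocol*

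**What the plan says.** Secondary objectives 1 to 3 (Protocol, Objectives) take PIF, inhalations per day and IV one at a time. Each lists three example cut-offs held for at least 2 consecutive days; the stated aim for PIF is "to identify an optimal threshold for characterizing trends in acute changes in the COPD Assessment Test (CAT"), and the other two use the same aim.

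The Planned Analysis list defines the reference event in item 5: "Frequency of CAT events (defined as increase in CAT score by 2 above Baseline CAT score"). Item 7 then widens the set of rules. It lists "Daily PIF 10, 20, 30 or 40% below Baseline PIF", three inhalation cut-offs (2, 4 or 6 above baseline) and "Daily PIF and/or Inhalations duration of 2, 3 or 4 or more days outside of Baseline". The methods named in item 7 are correlation and regression. IV is not part of item 7.

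The Statistical Analysis section says in general terms that "sensitivity/specificity/ROC analysis will be performed", calls all data exploratory, and allows additional analysis by the sponsor's biostatisticians. The Protocol Overview gives the size: "Twenty (20) patients with COPD requiring intermittent short acting beta agonist (SABA) rescue inhaler usage", with "a treatment period of 6 months" and CAT forms "to be completed at home on a weekly basis".

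The Protocol Overview also fixes one rule in advance. A patient is at risk when daily inhalations are at least 4 above baseline, or daily PIF is at or below 80% of baseline, or both, for 2 consecutive days.

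**The concern.** When several rules are tried and the best is kept, its score on the data used to pick it is, on average, higher than its score in new patients. Part of its lead is chance. The exploratory label removes the need for power and for control of the type I error. It does not remove this bias, which sits in the estimate itself.

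The performance of the chosen threshold is what a reader would carry forward from this pilot to a larger study or to practice. If only the apparent figure is reported, that reader cannot tell how much of it is selection.

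**Working it through.** **Inputs from the protocol.** 20 patients; 6 months, taken as 26 weeks; weekly CAT, so at most 20 × 26 = 520 patient-weeks; 4 PIF cut-offs, 3 inhalation cut-offs and 3 durations in item 7. The CAT event rate and the unit of analysis are not given. There is no stated power, rule count or expected sensitivity to reproduce.

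**Number of rules.**
- PIF alone: 4 × 3 = 12. Inhalations alone: 3 × 3 = 9. Single-parameter total: 21.
- PIF AND inhalations with one shared duration: 4 × 3 × 3 = 36. The same with OR: 36.
- One operator only: 21 + 36 = 57. Both operators: 21 + 72 = 93. Both operators with separate durations: 21 + 2 × (4 × 3 × 3 × 3) = 237.
- Examples in secondary objectives 1 to 3: 3 + 3 + 3 = 9.

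**Size of the bias.** The measure is the Youden index, J = sensitivity + specificity − 1. In each simulated trial of 20 patients the rule with the highest J among the 93 was picked, and its true J was read from a reference sample of 1,500 patients. Assumptions that are not in the protocol: day-to-day PIF standard deviation 15% of baseline with lag-1 correlation 0.6; 2 inhalations a day at baseline, Poisson with weekly variation; where an association exists, PIF falls by 10 points of baseline and inhalations rise 1.65-fold in event weeks.

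| Unit and event rate | No association: apparent vs true J | Association: apparent vs true J |
|---|---|---|
| Patient-week, 3% | 0.14 vs about 0 | 0.50 vs 0.32 |
| Patient-week, 8% | 0.09 vs about 0 | 0.45 vs 0.36 |
| Patient-week, 15% | 0.07 vs about 0 | 0.42 vs 0.37 |
| Patient-week, 30% | 0.05 vs about 0 | 0.42 vs 0.38 |
| One observation per patient, 30% | 0.26 vs about 0 | 0.60 vs 0.30 |
| One observation per patient, 50% | 0.24 vs 0.02 | 0.59 vs 0.33 |

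Unrounded, the patient-week gap runs from 0.415 − 0.385 = 0.030 to 0.503 − 0.324 = 0.179. With one observation per patient it runs from 0.238 − 0.019 = 0.219 to 0.601 − 0.304 = 0.297. At 3% event weeks with an association, nearly all of the gap is in sensitivity (0.74 apparent, 0.57 true); specificity is 0.76 in both.

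With events and signals clustered by patient, a 15% mean event rate and no association, mean apparent J was 0.07 to 0.09, with a 95th percentile of 0.13 to 0.24.

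**Dependence on the number of rules** (similar assumptions, 3 to 30% event weeks, events clustered by patient).
- No association, apparent J: 0.05 to 0.12 with 93 rules, 0.04 to 0.10 with 21, and 0.04 to 0.08 with the six PIF and inhalation examples in the objectives.
- Association at half strength, 3% event weeks: 0.31 vs 0.19 (93 rules), 0.26 vs 0.16 (21), 0.25 vs 0.17 (six).
- Only the three PIF examples searched: bias of 0.00 to 0.05.

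**Does resampling by patient repair it?** A separate simulation (120 replicates, correlated daily noise, CAT events with patient random intercepts) covered no link, a modest link and a stronger link. Apparent J was 0.059, 0.132 and 0.211. Leave-one-patient-out J was −0.005, 0.077 and 0.159. In 200 new patients J was 0.001, 0.077 and 0.155.

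**The case against.** Four points weigh on the other side.

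**The selection step is inferred.** A reader might take the plan to say that the best of 93 rules will be chosen by ROC. It does not. Item 7 names correlation and regression and chooses nothing, ROC is mentioned once in general, and the optimal threshold is sought one parameter at a time. The protocol states no rule count, and 93 is one reading beside 21, 57 and 237. This stands, so the point must be conditional: it applies if a threshold is chosen and scored on these patients.

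**The missing correction may be in the statistical analysis plan.** That document is not at hand, and resampling methods are often left to it. This also stands: the silence is not in itself an error. But the protocol does set out a grid of rules, the performance measures and an aim of finding an optimum, and nothing in it would keep the resulting figure free of selection bias.

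**The bias can be small.** With 15% event weeks there are about 0.15 × 520 = 78 event and 442 non-event weeks. With sensitivity 0.72 and specificity 0.70, the standard error of J before clustering is √(0.72 × 0.28/78 + 0.70 × 0.30/442) ≈ 0.055, about the size of the bias in that row (0.05). Relative figures can also mislead: 0.132 against 0.077 is about 70% too high, yet the gap is 0.055. This stands for common events. It fails for rare events or one observation per patient, and an interval centred on a biased estimate does not show the bias.

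**This is a pilot seeking potential thresholds, and one rule is fixed in advance.** Both are true. The at-risk rule carries no selection bias, which makes it a useful comparator. It does not protect the performance figure of any other rule that is picked as best.

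**Conclusion.** The point holds in conditional form. If a PIF, inhalation, IV or combined threshold is reported as optimal, and its sensitivity, specificity or AUC comes from the same 20 patients without correction, that performance is expected to be too high. For the 93-rule grid the expected excess is about 0.03 to 0.18 Youden at patient-week level and about 0.2 to 0.3 with one observation per patient. It shrinks as fewer rules are searched or CAT events become more common.

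The direction was the same in every scenario run with the full grid. The size rests on assumed noise, association and event rates, because the protocol gives neither the CAT event rate nor the unit of analysis. A reader might infer that the reported performance is certain to be materially inflated, or that the protocol is in error for not naming a correction. The documents support neither. This is a cheap improvement to the planned analysis, not a flaw in the design.

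**What to change.** Add to Planned Analysis item 7, or to the statistical analysis plan, for any PIF, inhalation, IV or combined threshold that is reported as optimal:

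- Name the selection criterion (for example the maximum Youden index against CAT events) and the unit of analysis (for example the patient-week). Resampling cannot be run without both.
- Repeat the whole selection, over cut-off, duration and and/or combination, in a leave-one-patient-out loop or a bootstrap that resamples patients. In the leave-one-out version, pool the predictions for the left-out patients before computing sensitivity and specificity, since some patients may have no event.
- Report optimism-corrected sensitivity, specificity and AUC beside the uncorrected values, and label the latter as apparent.
- State how many rules were searched and how often each was selected across resamples.
- Report the at-risk rule of the Protocol Overview as an unselected comparator. Score it against the scheduled weekly CAT, because extra CAT forms are administered whenever that rule is met.

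The cost is some extra programming and slightly less favourable reported performance. No new data, visits or procedures are needed.
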